10.2.2 ANALYSIS OF THE SECONDARY ENDPOINT(S)

1. Change in T cell exhaustion and/or inhibition following treatment
2. Change in serum immunoglobulin levels following treatment
3. Progression free survival (PFS) and association with immune biomarkers

To determine if T cell exhaustion or inhibition have change due to treatment with the combination therapy at baseline immune testing to immune testing following completion of pembrolizumab and ibrutinib treatments (week 52) using paired t-tests with the null hypothesis being that there is no change in immune measurements following treatment (i.e., $H_0: \mu_d = 0$). If the assumptions of normality do not hold upon assessment, we will instead use nonparametric t-tests (i.e., Wilcoxon Sign Rank Test). Similar tests will be used to determine if changes in serum immunoglobulin levels also resulted following treatment. Tests will be one-sided as based on biology expect the change in immune response to be in one direction following treatment. Tests will be considered statistically significant if the p-value is less than 0.05. Assuming the study go on to stage II and enroll 25 patients, we will be able to detect a modest effect size of 0.60. To determine the association of progression free survival (PFS) with immune biomarkers (T cell exhaustion and/or inhibition, serum immunoglobulin levels), Cox proportional hazards models will be fit with assumption of proportional hazards (PH) assumption check via Schoenfeld residuals. If the PH assumption does not hold, we will rely on use of non-parametric methods (Kaplan-Meier curve with log-rank tests) where the biomarkers will be dichotomized for analysis based on an optimal cut-point determination based on an outcome-oriented approach outlined by Contral and O'Quigley (Contal C, O'Quigley J. An application of changepoint methods in studying the effect of age on survival in breast cancer. Computational Statistics & Data Analysis. 1999;30:253-70.). A Cox regression of the log hazard ratio on the continuous biomarker (assuming a standard deviation of 1 and an anticipated event rate of 0.50) will have 80% power at a 0.05 significance level to detect a regression coefficient equal to 0.79 (i.e., hazard ratio of 2.20).

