7.1.13 Correlative Studies Blood Sampling

Blood samples will be collected pre-dose on Day 1, Week 6, Week 21, and end of ibrutinib therapy for immune testing per Schedule of Events. They will be performed at investigator's discretion if early study termination. For sampling requirements, see Section 7.2.

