10.2 DESCRIPTION OF STATISTICAL METHODS

10.2.1 ANALYSIS OF THE PRIMARY EFFICACY ENDPOINT(S)

The Simon's minmax two-stage design will be used to test the null hypothesis that complete response (CR) \leq 10% versus the alternative that CR \geq 30% with 90% power and a type I error rate of 10%. This will result in an expected sample size of 20.37 and a probability of early termination of 0.52. After testing the drug combination on 16 patients in the first stage, the trial will be terminated if 1 or fewer respond. If the trial goes on to the second stage, a total of 25 patients will be studied. If the total number responding is less than or equal to 4, the drug combination will be rejected. Statistical analyses will be descriptive in nature. Patients' demographics, AEs and serious AEs, disease status, and CR will be summarized by descriptive statistics.

Clinical response rates will be calculated with 95% CIs.

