10.2.4 EXPLORATORY ANALYSES

Biological samples for each of the 25 patients enrolled in the trial will be collected at 4 time-points. As the correlative experiments are not the primary focus of the study and are more exploratory in nature, no sample size / power calculations were completed. Summary statistics will be used to summarize the quantitative measures (e.g., cytokine levels, expression levels) for the patients at the 4 time-points with two-sample t-test use to determine if quantitative measurements differ between patients that response and patients that do not response at each time point. When assessing changes in quantitative measurements between time-points (e.g., pre and post treatment measurements) paired t-tests will be used. Longitudinal analysis with linear mixed models will also be used to look for statistical differences between the responders and non-responders using quantitative measurements at all 4 time-points. Correlation between quantitative measurements will be assessed with Spearman correlation.

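### The week-52 immune-change test relies on a blood sample that is optional after early termination, with no missing-data method, so it is at risk of selection bias of unknown size and direction.

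*Combined protocol and SAP*

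**What the plan says.** Section 10.2.2 sets the change in T-cell exhaustion or inhibition from baseline to the end of both drugs, which it places at week 52, as the quantity to be tested. It does so "using paired t-tests with the null hypothesis being that there is no change in immune measurements following treatment". A Wilcoxon signed-rank test replaces the t-test if normality fails, and similar tests apply to serum immunoglobulins. On sidedness: "Tests will be one-sided as based on biology expect the change in immune response to be in one direction following treatment". On the threshold: "Tests will be considered statistically significant if the p-value is less than 0.05". On size: "Assuming the study go on to stage II and enroll 25 patients, we will be able to detect a modest effect size of 0.60". The power behind that statement is not given.

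Section 7.1.13 schedules correlative blood at day 1, week 6, week 21 and the end of ibrutinib, but leaves it to the investigator's "discretion if early study termination". The End of Treatment visit list (7.3.2.11) and note 12 to the schedule (7.3.7) say the same. Section 10.2.4 nevertheless states that each of the 25 patients will be sampled at four time points.

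For missing data, Section 12 provides database queries and Section 10 provides nothing. Section 10.1 defines who is evaluable for response and uses that set for efficacy and safety, but does not address a patient who lacks the end sample. Section 10.2.4 does say "Longitudinal analysis with linear mixed models will also be used", but to compare responders with non-responders; for pre/post change that section also uses paired t-tests.

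**The concern.** A paired test discards every patient without the end value, along with that patient's intermediate samples. Section 5.4.1 lists unacceptable adverse events, intercurrent illness and noncompliance among the reasons for discontinuation, and its follow-up text also refers to progressive disease. These reasons could well be related to immune course. The trial is open-label, so the investigator who decides whether to draw the tube knows why the patient stopped.

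If patients without an end sample had the less favourable immune course, the mean change among those who remain is too favourable, and a one-sided test turns that directly into false claims. Improving immune function is the aim named in the trial's title, and immune restoration is a listed secondary objective. Loss of pairs also reduces power, whatever its cause.

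**Working it through.** **1. The plan's own figure.** Inputs from 10.2.2: n = 25, standardized effect d = 0.60, one-sided 0.05. For a paired t-test, power = P(T > t(0.95, n−1)), where T is noncentral t with n−1 degrees of freedom and noncentrality d√n. Here d√n = 0.60 × 5 = 3.0 and power = 0.898. The effect detectable with 90% power is 0.603. So 0.60 reproduces as one-sided 0.05 with about 90% power, provided all 25 pairs are complete.

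**2. Fewer pairs.** The documents give no missing-sample rate, so the losses are assumptions. For scale only, 10.2.3 takes 20% as the maximum allowable unacceptable toxicity rate, and 0.20 × 25 = 5 patients.

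| Complete pairs | Power at d = 0.60 |
|---|---|
| 25 | 0.90 |
| 22 | 0.86 |
| 20 | 0.83 |
| 18 | 0.79 |
| 15 | 0.71 |

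The plan also allows a stop at stage 1: "After testing the drug combination on 16 patients in the first stage, the trial will be terminated if 1 or fewer respond". With 16 complete pairs, power is 0.74.

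**3. Bias, general form.** Score change so that positive is favourable. Let q be the share without an end sample, and g the mean change in patients with a sample minus the mean change in those without. The all-patient mean is (1−q)·m(with) + q·m(without), so the completers' mean exceeds it by q × g. Type I error is from 40,000 simulated trials per case, 25 patients, no true overall change; q and g are assumed.

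| q | g (SD) | Bias = q × g (SD) | One-sided type I error |
|---|---|---|---|
| 0.20 | 0 | 0 | 0.05 |
| 0.20 | 0.5 | +0.10 | 0.11 |
| 0.20 | 1.0 | +0.20 | 0.24 |
| 0.40 | 0.5 | +0.20 | 0.19 |
| 0.20 | −0.5 | −0.10 | 0.02 |

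**4. Bias through the week-21 value.** Assume no true change, 25 patients, correlation r between week-21 and end changes, and loss of the end sample with probability L among the worst share w at week 21. Mean pairs = 25(1 − wL). Spurious mean change = r·φ(z_w)·L/(1 − wL), where φ is the normal density at the w quantile (0.280 for w = 0.20, 0.348 for w = 0.30). For the first row: 0.6 × 0.280 × 0.8/0.84 = 0.16. Rejection rates are from 20,000 simulated trials per case.

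| w | L | r | Mean pairs | Spurious change (SD) | Paired test rejects |
|---|---|---|---|---|---|
| 20% | 80% | 0.6 | 21 | 0.16 | 18% |
| 30% | 80% | 0.6 | 19 | 0.22 | 25% |
| 20% | 50% | 0.6 | 22.5 | 0.09 | 11% |
| 20% | 30% | 0.6 | 23.5 | 0.05 | 8% |
| 20% | 80% | 0.3 | 21 | 0.08 | 10% |
| 20% | 80% | 0 | 21 | 0 | 5% |

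**5. What a likelihood analysis recovers.** In the first two rows, an analysis that also uses the week-21 value rejects in about 5.5% to 5.9%. That is expected, because loss was made to depend only on an observed value. If loss depends instead on the unobserved end value (same L = 80%, w = 20% to 30%, r = 0.6), that analysis still rejects in about 25% to 39%.

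**The case against.** The strongest reply is that a risk is not a result. A reader might infer that the immune result is biased toward patients who did well and would make an ineffective regimen look restorative. The documents do not support that. They give no dropout rate, no missing-sample rate and no link between stopping and immune markers. Discretionary does not mean absent: the End of Treatment visit covers early termination and lists the tube. Patients stopping for immune-related toxicity could have larger T-cell changes (an inference, not in the documents), which would reverse the bias. This objection stands, and it limits the point to a risk whose size and direction are unknown.

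A reader might also take 18% to 25% as the expected false-positive rate. Those are the severe cases; milder assumptions give 5% to 11%. Nor is it right that the detectable effect is simply 0.68 instead of 0.60: 0.68 needs an assumed loss of five pairs and 90% power, which 10.2.2 does not state.

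Two further points have some weight. Section 5.4.2 allows replacement of patients who drop out before 9 weeks, which partly protects the number of pairs but not against selection. And immune change is secondary: the go/no-go decision rests on complete response (10.2.1), which this does not affect.

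Finally, the mixed model in 10.2.4 is not a ready-made cure. It is planned only for responder comparisons, and using it here is a new specification. None of these replies supplies a rule for patients without the end sample.

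**Conclusion.** The point holds as a risk of selection bias with no plan to detect or correct it. Across the assumed range (30% to 80% loss among the worst 20% to 30% at week 21, correlation 0 to 0.6), the nominal 5% test rejects in about 5% to 25% under no true change. There is no inflation if patients with and without samples do not differ, and the error falls below 5% if those without changed more favourably. The 0.60 figure is correct for 25 complete pairs only; at an assumed 20 pairs, power for that effect is 0.83. The change is worth making because immune restoration is a central claim of the trial and the remedy is cheap.

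**What to change.** - **Sampling.** Make the correlative sample routine at the End of Treatment visit, including early termination, in 7.1.13, 7.3.2.11 and 7.3.7 note 12. State whether a sample taken 0 to 7 days after an early last dose counts as the post-treatment value, since 10.2.2 names week 52.
- **Analysis.** In 10.2.2, define the analysis set and estimate the baseline-to-end change with a linear mixed model for repeated measures, using all patients and all available samples. Keep the paired test on completers alongside it, and add a sensitivity analysis for departure from missing at random.
- **Size.** State that 0.60 assumes 25 complete pairs, and give the power.
- **Consistency.** Reconcile the sampling weeks, because the model depends on them: 7.1.13 and 7.3.7 note 12 give weeks 6 and 21, while 7.2 gives weeks 9 and 12.

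The cost is SAP and protocol wording and a few extra research tubes (about 50 cc per draw, 7.2) at a visit that already takes blood. The model relies on missing at random and recovers less for patients who stop before week 21: on the 7.1.13 schedule they have only baseline and perhaps a week-6 sample, drawn at the visit where ibrutinib starts.

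### If proportional hazards fails, keep the biomarker continuous and model its change over time; an outcome-chosen cut-point with a log-rank test is the weaker fallback (minor)

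*Combined protocol and SAP*

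**What the plan says.** Section 10.2.2 fits Cox models of progression-free survival (PFS) on continuous immune biomarkers ("T cell exhaustion and/or inhibition, serum immunoglobulin levels"), with a proportional-hazards (PH) "assumption check via Schoenfeld residuals". It gives no threshold for that check. It then says: "If the PH assumption does not hold, we will rely on use of non-parametric methods (Kaplan-Meier curve with log-rank tests". In that branch "the biomarkers will be dichotomized for analysis based on an optimal cut-point determination based on an outcome-oriented approach", with a reference to a published changepoint method.

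The only power figure for the PFS analysis belongs to the continuous Cox model. Under "assuming a standard deviation of 1 and an anticipated event rate of 0.50", it "will have 80% power at a 0.05 significance level to detect a regression coefficient equal to 0.79 (i.e., hazard ratio of 2.20". The sample size comes from earlier in the same section: "Assuming the study go on to stage II and enroll 25 patients".

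The section does not give power for the fallback, a minimum group size, or a significance level for the log-rank test. It does not say whether the cited method's search-corrected p-value will be used, whether a hazard ratio will be reported at the chosen cut, or how an effect that changes over time will be described.

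**The concern.** Three features of the fallback look wrong for its purpose.

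- Splitting a continuous biomarker into two groups throws away information when there are only about 12 events.
- The two-group log-rank test is the score test of a Cox model with a binary covariate. It remains valid under its null without PH, but it is weak when an effect fades or reverses. Changing to it therefore does not address the problem that triggered the change, and the time pattern stays unmodelled.
- The cut is the one that best separates the outcome, so the displayed curves are selected to look far apart.

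At stake is a secondary finding. A biomarker threshold from 25 patients could be carried into later work on the strength of an exaggerated picture, or a real time-dependent association could be missed.

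**Working it through.** **Inputs.** From Section 10.2.2: n = 25, event rate 0.50 (25 × 0.50 = 12.5 events), biomarker SD 1, coefficient 0.79. From the Study Summary: two years per participant, used as a 24-month horizon. Assumed, because the documents do not give them: a normal biomarker, exponential or piecewise hazards, a PH check at the 5% level (a rank-time test standing in for Schoenfeld residuals), and either at least 3 patients per group or cuts between about the 10th and 90th percentiles.

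**1. The plan's own figure.** Detectable coefficient = (z for alpha + z for power) / (SD × √events).
- Two-sided: (1.960 + 0.842) / √12.5 = 2.802 / 3.536 = 0.792, a hazard ratio of 2.21. Power at 0.79 is 79.8%. This reproduces the plan.
- One-sided: (1.645 + 0.842) / 3.536 = 0.703. This does not. The sentence "Tests will be one-sided as based on biology expect the change in immune response to be in one direction following treatment" sits with the paired change tests.

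The figure is right for the continuous Cox model. It does not carry over to the fallback.

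**2. How often a null biomarker reaches the fallback.** A biomarker unrelated to PFS satisfies PH, so it gets there only by a false alarm: 5.1% of 4,000 simulated null trials, and 646 of 12,000 (5.4%) in a second run. Section 4.1 names eight exhaustion markers. If all eight were null and independent, the chance that at least one reaches the fallback is 1 − 0.95⁸ = 34%.

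**3. What the fallback shows for those null biomarkers.**
- The median hazard ratio at the chosen cut (folded above 1) is 3.2 to 3.5 across runs. Without any trigger, a fixed median split would give about 1.5 by chance: SE of log HR = 2/√12.5 = 0.566, and exp(0.674 × 0.566) = 1.46.
- An uncorrected log-rank test at that cut rejects in 43% to 48%.
- The cited method's corrected p-value rejected in 5.9% of 85 such datasets.

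**4. Type I error of the whole procedure.** In the 4,000-trial run it was 6.9% with an uncorrected log-rank and 4.8% with the corrected p-value. The parts agree: the fallback contributes 0.051 × 0.48 = 2.4%, leaving about 4.5% from the Cox branch.

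**5. Power when hazards are not proportional.** Each test was run on every dataset and calibrated to 5% size (1,500 runs per row). The time-varying model is a 2-df test of the continuous biomarker plus its interaction with event-time rank.

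| Log HR per SD, before / after change | Change at (months) | Optimal-cut log-rank | Continuous Cox | Continuous, time-varying | PH check rejects |
|---|---|---|---|---|---|
| 0.79 / 0 | 8 | 16% | 22% | 26% | 17% |
| 1.2 / 0 | 8 | 31% | 48% | 59% | 31% |
| 0 / 0.79 | 8 | 24% | 30% | 35% | 21% |
| 0.79 / −0.79 | 11 | 7% | 7% | 45% | 55% |
| 1.5 / −1.5 | 11 | 17% | 13% | 88% | 90% |

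A separate simulation with a log(time) interaction, in four further non-proportional scenarios, gave 68% vs 66%, 43% vs 18%, 36% vs 28% and 69% vs 56% in favour of the time-varying model. The first of these margins is negligible.

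**6. A limit on the alternative.** The 2-df test shares its interaction component with the PH check. Among the 85 null datasets that failed the check (5.7% of 1,500), it rejected in 45.9%, contributing 0.057 × 0.459 = 2.6%. The uncorrected log-rank contributed 0.057 × 0.435 = 2.5%. A 2-df p-value computed only after a failed check therefore offers no better error control. The gain lies in power, in describing the time pattern, and in dropping the selected display.

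**The case against.** The strongest reply is that the branch is rarely reached, is not the plan's main PFS analysis, and names a published method that has its own corrected p-value. Section 10.2.1 calls the analyses descriptive, and no decision depends on this one. All of that stands, and it is why the point is minor. A further fair reply is that an interaction adds a second parameter on about 12 events. That also stands.

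Three stronger readings are tempting, and the documents do not support them.

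- **A null biomarker will usually be shown with a hazard ratio near 3.** Applying the cut to every null dataset does give a median of about 3.0. The plan applies it only after PH fails. Under a 5% check, a null biomarker reaches the fallback with a hazard ratio of at least 2.2 in 4.6% of trials, about 1 in 20. A looser or visual check would raise this. Nor does the plan promise a hazard ratio in this branch; the figure describes any that is computed there, and indicates how far apart the curves will look.
- **The plan tests the log-rank at 0.05.** It does not say so. One 0.05 closes the text on paired change tests; the other belongs to the Cox power statement.
- **The fallback always loses power against the continuous Cox model.** A comparison under proportional hazards is beside the point, because the fallback is not used there. Under crossing hazards the cut-point test equals the plain Cox model (7% vs 7%) or is slightly ahead (17% vs 13%). The consistent loss is against a model that lets the effect change with time.

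**Conclusion.** The concern holds as a cheap improvement of minor severity. When the fallback is triggered by a null biomarker, the chosen cut gives a median hazard ratio of about 3.2 to 3.5, and an uncorrected log-rank rejects in 43% to 48%. Over the whole procedure the type I error is only slightly raised, to about 7% uncorrected, and is about 5% with the corrected p-value. In every non-proportional scenario run, a continuous time-varying model had at least as much power as the optimal cut, with margins from 2 to 71 percentage points. These results rest on a normal biomarker, about 12.5 events, the assumed change points and group-size limits, and a 5% PH check. The primary complete-response decision is unaffected.

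**What to change.** Reword the fallback in Section 10.2.2:

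- State how Schoenfeld residuals will be judged. If they indicate non-proportionality, keep the biomarker continuous and add a biomarker-by-log(time) term, reporting the effect over time with intervals; or report an average effect with a robust standard error.
- If a p-value is wanted from the joint 2-df test, specify that test in advance for every biomarker. If it is run only after a failed check, present it as descriptive.
- Show Kaplan-Meier curves by a median split, for display only.
- Delete the optimal cut-point step. If it is kept, label it hypothesis-generating, use the cited method's search-corrected p-value, state a minimum group size, and report no hazard ratio.

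The cost is wording. If the cut-point step is deleted, the trial proposes no threshold. The time-varying estimate will be imprecise, with one extra parameter on about 12 events.

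### The 80% power stated for the PFS–biomarker Cox model at HR 2.20 is a large-sample approximation that is too optimistic at about 12 events; simulated power is about 65–73% with a normally distributed biomarker

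*Combined protocol and SAP*

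**What the plan says.** Section 10.2.2 plans Cox proportional hazards models relating PFS to T-cell exhaustion or inhibition markers and to serum immunoglobulin levels. Its closing power statement claims that such a model, fitted to a biomarker on its continuous scale, "will have 80% power at a 0.05 significance level to detect a regression coefficient equal to 0.79 (i.e., hazard ratio of 2.20". Two inputs are named for this claim, in a parenthesis: "assuming a standard deviation of 1 and an anticipated event rate of 0.50".

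The claim gives no sample size. The number comes from an earlier power statement in the same section, "Assuming the study go on to stage II and enroll 25 patients", and agrees with Section 10.2.1: "If the trial goes on to the second stage, a total of 25 patients will be studied".

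The section is also silent on whether the Cox test is one- or two-sided. Its sidedness statement, "Tests will be one-sided as based on biology expect the change in immune response to be in one direction following treatment", belongs to the before-and-after tests of immune measures. The section names no power formula, biomarker distribution, censoring pattern or test statistic (Wald, score or likelihood ratio) for the Cox analysis.

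**The concern.** The printed pair of coefficient and power is what the large-sample event formula gives. That formula treats each event as carrying information equal to the full biomarker variance, here 1, which is accurate when the hazard ratio is close to 1 and the risk sets are large. Neither condition holds here. At HR 2.20 per SD, patients with high biomarker values tend to fail first, so the spread of the biomarker among those still at risk shrinks, and with 25 patients the risk sets are small from the start. Information per event then falls below 1 and power falls with it.

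At stake is the only sensitivity statement given for this listed secondary analysis. Someone interpreting a null result would take the chance of missing HR 2.20 per SD to be 20%. If the simulated figures are right, that chance is about 27–30% under a common cut-off and 32–35% under random censoring, even with all 25 patients enrolled and half having events.

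**Working it through.** **Inputs from the plan.** Coefficient 0.79 per SD (exp(0.79) = 2.20), SD 1, event rate 0.50, alpha 0.05 and power 80%, all from Section 10.2.2. N = 25, carried over from the preceding sentence of that section. Expected events: 25 × 0.50 = 12.5.

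**Step 1: reproduce the plan's figure.** For a continuous covariate, events D = (z_alpha + z_power)² / (SD² × coefficient²).

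- Two-sided 0.05, events needed: (1.960 + 0.842)² / 0.79² = 12.58, so N = 12.58 / 0.50 = 25.2.
- Two-sided 0.05, power at 12.5 events: Φ(0.79 × √12.5 − 1.960) = Φ(0.833) = 79.8%.
- Two-sided 0.05, coefficient for 80% power: 2.802 / √12.5 = 0.792 (HR 2.21).
- One-sided 0.05: power would be 87.5%, and the coefficient for 80% would be 0.70 (HR 2.02).

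The printed figure is therefore the two-sided formula result.

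**Step 2: simulate the Cox test.** Each trial has 25 patients, exponential PFS with hazard proportional to exp(0.79x), true proportional hazards, and censoring set to give 12.5 events on average. There were 30,000 trials per row. Biomarker shape and censoring pattern are assumptions, because the plan gives neither. All shapes have population SD 1. The table shows two-sided 0.05 power at HR 2.20.

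| Biomarker | Censoring | Wald | Score | Likelihood ratio |
|---|---|---|---|---|
| Normal | Common cut-off | 70.6% | 71.9% | 72.9% |
| Normal | Staggered follow-up | 69.9% | 71.3% | 72.2% |
| Normal | Random exponential | 64.5% | 66.5% | 67.8% |
| Uniform | Common cut-off | 71.6% | 74.3% | 74.4% |
| Uniform | Random exponential | 65.9% | 69.3% | 69.7% |
| Two-point | Common cut-off | 65.9% | 74.9% | 74.9% |
| Two-point | Random exponential | 59.2% | 71.2% | 71.1% |
| Lognormal (right-skewed) | Common cut-off | 76.5% | 78.0% | 74.3% |
| Lognormal (right-skewed) | Random exponential | 70.8% | 72.9% | 69.1% |

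Standardising a normal biomarker within each sample raises the common cut-off figures to about 73% (Wald) and 75% (likelihood ratio). Standardising a right-skewed biomarker within the sample, with its long tail at high hazard, gives about 84% and 81.5%. That is the one case reported to reach 80%.

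**Step 3: check the cause.** With no true effect, a normal biomarker and a common cut-off, rejection rates are 5.2% (Wald), 5.6% (score) and 5.8% (likelihood ratio), so the loss is not due to a conservative test. At coefficient 0.79 with a normal biomarker, information per event is about 0.72 under a common cut-off and 0.63 under random censoring, against the formula's 1.

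**Step 4: find the HR that gives about 80%** (normal biomarker, two-sided 0.05).

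| HR per SD | Censoring | Wald | Score | Likelihood ratio |
|---|---|---|---|---|
| 2.40 | Common cut-off | 77.9% | 79.0% | 80.0% |
| 2.45 | Common cut-off | 79.4% | 80.5% | 81.5% |
| 2.50 | Common cut-off | 81.2% | 82.1% | 82.8% |
| 2.60 | Random exponential | 78.4% | 79.9% | 80.9% |
| 2.70 | Random exponential | 81.1% | 82.6% | 83.6% |

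**The case against.** The strongest reply is that nothing has been miscalculated. The formula is standard and the plan's inputs return its printed answer. This stands: a reader might infer an arithmetic error, and the documents do not support that. What fails is the attribution of the formula's answer to the Cox test at this event count.

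A second reply is that 25 patients, 50% events and SD 1 do not fix the power. This also stands. A reader might infer that a figure such as 71–73%, or a detectable HR of 2.45, follows from those inputs alone. It also needs a biomarker distribution, a censoring pattern and a test, none of which the plan gives, so a range with named assumptions is all that can be claimed.

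A third concerns sidedness. A one-sided 0.05 Cox test with a normal biomarker has simulated power of about 77–83%, close to the printed 80%. But the plan's one-sided statement is attached to other tests, and the formula would then have printed a coefficient of 0.70. The printed pair is a two-sided figure.

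A fourth is that the correction is no larger than the uncertainty in the event rate: by the plan's own formula, 10 events instead of 12.5 gives Φ(0.79 × √10 − 1.960) = 70.5%. This is fair on priority, but it does not make the printed figure correct on its own inputs.

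It is also tempting to recommend the likelihood-ratio test because it appears to gain about 2 points. Most of that gain is inflated type I error. In a 40,000-trial run (normal biomarker, common cut-off), power was 72.8% against 70.4% for Wald, with null rejection of 5.8% against 5.2%. With both held to a true 5%, power is 70.4% and 69.8%.

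**Conclusion.** The point holds as a limited correction. The stated 80% is a two-sided large-sample result that overstates what the Cox test delivers with about 12 events at HR 2.20. With a normal biomarker, the shortfall is about 7–10 points under a common administrative cut-off and about 12–15 points under random censoring. The direction is the same for most biomarker shapes tried, with the within-sample-standardised right-skewed case as the exception. All figures grant the plan its 25 patients, its 50% event rate and proportional hazards; none of these is disputed here.

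The weight is modest. A reader might infer that the trial is underpowered or wrongly sized; the documents do not support that. The 25 patients come from the two-stage design on complete response in Section 10.2.1, and no stopping rule or decision rule depends on the PFS–biomarker model. Nor does the plan say that a null result would be taken to exclude HR 2.20. That is a risk in how the sentence may be read.

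**What to change.** Replace the Cox power sentence in Section 10.2.2 with one that states N, events, sidedness, the simulated power and its assumptions. For example:

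> With 25 patients and about 12 PFS events, a two-sided 0.05 test in the Cox model has about 70–73% power for HR 2.20 per SD and about 80% power for HR 2.4–2.5 per SD (simulation; normally distributed biomarker, common administrative censoring). With random censoring, power at HR 2.20 is about 65–68%.

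If the expected biomarker distribution is known to be skewed, or the biomarker will be standardised within the sample, rerun the simulation on that basis and say so. No preference for the likelihood-ratio test need be added.

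The cost is one sentence of statistical text and a slightly less favourable stated figure. No patients, visits or data are added, and the primary design does not change.
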